
## Data & Safety Monitoring

- Summarize safety concerns, and describe the methods to monitor research subjects and their data to ensure their safety, including who will monitor the data, and the frequency of such monitoring. If a data monitoring committee will be used, describe its operation, including stopping rules and frequency of review, and if it is independent of the sponsor (per 45 CFR 46.111(a) (6)).

This research study carries minimal risk. All patients in the study will continue their usual care during the course of this trial, thus their doctors will provide monitoring of the patients' overall medical status. All research personnel who have direct contact with patients will be trained to observe and report any adverse event to the principal investigator (PI). The PI will report any adverse events to the institutional review board (IRB) at Duke University and to NIH. An adverse event is defined as any untoward medical occurrence during the clinical investigation that has a causal relationship to the study protocol. A serious adverse event is defined as any event which results in death, is immediately life threatening, results in persistent or significant disability/incapacity, patient hospitalization, or is serious for any other reason representing significant hazard. We will also appoint one data safety officer who is a physician (MD) and not associated with this study. The appointed MD officer will have experience with clinical research and trials with oncology populations and have a thorough understanding of adverse events. The appointed data safety officer will also have technology expertise and will have an annual responsibility to evaluate our current methods of assessment and intervention and identify any problems.

All adverse events will be reported to Duke's IRB and the data safety officer in real-time. All data will be stored on a secure server with multiple backups created regularly. All interactions with study participants will be under the direction of a licensed clinical psychologist (PI: [name]). [name] is supported by a strong and experienced team of investigators, including [name], a senior investigator and licensed clinical psychologist. Study investigators and staff for this trial will be taught to monitor for any signs that participants are experiencing high levels of physical or emotional distress that need to be addressed outside the context of this trial. If this is determined to be the case, the PI will work directly with the participant to move forward in a way that is in the best interest of the patient. No participant will be kept in the trial if they are experiencing increased or extreme distress. [name] works directly with Cancer Patient Support and Care at Duke Cancer Institute as a practicing licensed clinical psychologist and as a supervisor to psychology trainees (i.e., advanced graduate students, clinical psychology doctoral interns); she is integrated into the psychosocial care program at the Cancer Center and has experience referring cancer patients who are distressed to appropriate psychosocial or psychiatric care within this large team of mental health professionals. She will use the same resources when making referrals for distress participants in this study.

**Potential Risks.** Risks associated with the proposed study are minimal and rare. Psychological risks include anxiety or distress due to questioning about thoughts, feelings, and personal/family history of cancer. There is the possibility of a breach of confidentiality due to the use of mailing of information. The consent form will address this possibility. All efforts will be made for confidentiality to be maintained by using case numbers to identify participants' research records and by having a limited number of individuals with access to identifying information. Identifying information will be kept separate from research records. All research records will be kept in a locked file cabinet and password protected computer files. Only the PI and other trained staff will have access to the research records. To ensure that there are no changes in potential risk during the course of the study and that confidentiality is maintained the PI and sponsors will implement a Data and Safety Monitoring Plan.

The primary risks of this study are those associated with confidentiality. There is some risk attendant to confidentiality of self-report data. Two password-protected databases will be used for this study to ensure confidentiality. First, a tracking database will be used for recruitment and follow-up. This data will house information related to tracking the participants in the study, such as MRN, name, phone numbers and addresses. No medically sensitive or outcome data will be stored in this database. This database will also track non-participants (i.e., those who have declined participation) only to the barest minimum to ensure that they are not contacted again about participation. At the end of the study, all identifiable data of non-participants such as their names will be deleted. Tracking data on participants will be retained for the usual required period. Second, all study data will be stored in a separate password protected database without any personal identifiers. Data in this database will be derived from patients' direct input into the electronic patient reported outcomes system (e.g., REDCap), which is an online survey system; data entered into this system is stored on a secure server housed behind the Duke University Medical Center (DUMC) firewall. Only a unique study identification number will link the electronic data to the study data file. The tracking data and study data will be stored in a file on a secure DUMC psychiatry server which can only be accessed by necessary members of the research team. Access to the Duke network requires a password protected, 128-bit encrypted virtual private network connection provided by Cisco systems.

**Mobile App Data Storage and Security.** Pattern Health (Durham, NC) is a digital health company specializing in patient centered web and mobile products for clinical and medical research and health data tracking and analysis, with expertise working with wireless devices and improving patient engagement. Pattern Health has an established relationship with researchers at Duke and is contracted for the development of a mobile app for use in the current study. Pattern Health will have access to PHI. Study personnel will input participant information including name, phone number, email, birth date, language preference, time zone, and gender to create a profile for the participant. Participants will enter their full name, date of birth and e-mail address to access the corresponding profile. MAG and ISO have reviewed and approved Pattern Health's documents outlining this data collection process, and data storage and security. The RDSP and corresponding exception requests for this will go through full approval. A contract will be executed between Pattern Health and Duke. Patients may enter assessment data via the study mobile app or on their own online or by phone with a study team member. Assessment data entered via the mobile app will be temporarily stored on the cloud-based app platform (Pattern Health) and imported to REDCap via an assigned study ID number. Assessment data will be transported from the cloud-based app into REDCap for storage. Pattern Health uses a MySQL database. This is a standard security feature, which allows the database to be kept separate from the web server to protect access to the database. In addition, the hard drive of the data base machine will be encrypted, which will provide security in case the hard drive is physically compromised.

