We have developed and tested numerous cognitive behavioral pain coping skills training protocols that enhance the abilities of patients with chronic disease to manage their pain, leading to improvements in pain and other important pain-related outcomes. Our group has extended this research by designing and testing pain coping skills protocols that use mobile health (mHealth) technology for cancer patients with pain. These protocols focus on decreasing patient burden and increasing patient accessibility and engagement by creating shorter protocols (4-6 sessions), using hybrid in person and videoconferencing methods, and using mHealth strategies (e.g., websites, smartphones, text messaging, real-time data collection with personalized feedback) to reduce intervention barriers (e.g., in person sessions). These mHealth pain coping skills interventions have shown high patient acceptability, feasibility, and efficacy. We published a large trial (N=178) showing a 4 session behavioral cancer pain intervention delivered with home-based videoconferencing is just as efficacious as a protocol delivered in person at the medical center. Importantly, the videoconferencing protocol showed significantly greater feasibility (i.e., attrition [16% vs. 30%], adherence) than the in person protocol.

Use of mHealth strategies and videoconference delivered behavioral pain interventions can improve patient access and decrease patient burden. However, videoconference delivered protocols retain some access barriers for many patients due to the therapist-led delivery model and resources required (e.g., expert pain therapist, scheduled appointments). Much more is needed to improve access for the greater than 22 million cancer survivors expected over the next 10 years. Developing additional behavioral approaches to cancer pain management is critical. A standalone behavioral cancer pain mobile application that uses efficacious cognitive and behavioral pain management strategies is likely to dramatically increase access to such interventions. A standalone app would eliminate the need for a therapist, be available to the patient at all times, and be easily accessible on a smartphone or tablet. Mobile apps also offer increased options for real-time personalization (e.g., messaging based on daily pain assessment) which can increase engagement and improve overall outcomes.

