
**Videoconference Delivered Pain Coping Skills Training (PCST-Video).** Participants randomized to PCST- Video will receive 4 behavioral cancer pain intervention sessions delivered by videoconferencing by

a pain therapist in the medical center to the patient in their natural environment (e.g., home). Sessions will be scheduled weekly for 45-60 min and mimic in person sessions. In rare circumstances when the participant is not able to connect via videoconferencing, the PCST-Video sessions can be delivered via phone. This is a backup option that will rarely if ever be used due to extenuating circumstances. PCST-Video session content is based on Pain Coping Skills Training (PCST) designed by [name] (mentor to Drs. [name] and [name]) and matches the PainPac skills modules described above. PCST-Video participants will complete assessments at the same intervals as PainPac participants. Interventionist Training (months 2-4). PCST-Video will be delivered by a masters or doctoral level psychologist with experience delivering behavioral pain interventions. Drs. [name] and [name] will provide training and therapists will be certified (>90% ratings of competence and protocol adherence) to deliver the intervention. Therapists will follow a manualized protocol; treatment strategies will be taught through didactic instruction, audio-/video-recorded illustration from model cases, and role-play of common scenarios. Sessions will be recorded and reviewed in supervision by [name]. Procedures to Ensure Consistency of Treatment. 1) The therapist will follow a manual; 2) Weekly supervision will occur; 3) Session recordings will be reviewed and feedback provided; and 4) Ratings of treatment adherence and competence will be conducted. Treatment Adherence and Therapist Competence. Ratings of protocol adherence will be made by Drs. [name] and [name]. Protocol adherence criteria will be developed for each session with satisfactory adherence ≥90% on the rating scale. Ratings of therapists' competence will be used to evaluate 20% of PCST-Video sessions.

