**Emotional Upset.** The risk of emotional upset associated with intervention sessions and assessments is rare, and all interactions with study participants will be under the direction of PI [name], a licensed clinical psychologist. To address risks related to the possibility of psychological distress, participants will have the option of withdrawing from the study without loss of benefit. Interventionists and study staff in this trial will have experience working with distressed patients with chronic disease. They will be trained, specifically in the context of this trial, to monitor participants' psychological status and for any signs that participants are experiencing high levels of physical or emotional distress that need to be addressed outside the context of this trial. Interventionists will be trained to report any concerns immediately and directly to the PI. If this is determined to be the case, the PI will work directly with the participant to move forward in a way that is in the best interest of the patient. No participant will be kept in the trial if they are experiencing increased or extreme distress. As noted previously, intervention sessions will be audio-recorded and reviewed by Drs. [name] and [name] to ensure the delivery of effective and ethical treatment. Further, the study Clinical Research Coordinators (CRC) will monitor daily all assessments with particular attention paid to the suicidal ideation item on the Brief Symptom Inventory. The CRC will immediately report all elevated responses on this item to the study PI. [name] (PI) will also be contacted when *any* emotional distress is identified in a participant. The study assessments have been well validated for use with patients with cancer. *Moreover, these assessments were specifically chosen for their brevity in order to reduce patient burden.* Participants will be reminded that they can omit responses to any questions that they do not feel comfortable answering. Again, all research personnel who have direct contact with patients will be trained to observe and immediately report any adverse events to [name]. [name] will report any adverse events to the institutional review board at Duke University and to NIH, and will consult Drs. [name] (licensed clinical psychologist and senior level faculty Co-I), and [name] (experienced physician) to collaboratively develop a course of action, which may involve facilitating referrals for additional treatment. These referrals may be made to various members of the Duke Cancer Patient Support Program, including psychiatrists, psychologists, and medical family therapists, as appropriate. Participants will be provided with emergency contact numbers as well as access to numerous support services offered through the DCI. [name] works directly with Cancer Patient Support and Care at Duke Cancer Institute as a practicing licensed clinical psychologist and as a supervisor to psychology trainees (i.e., advanced graduate students, clinical psychology pre-doctoral interns) and [name] (Co-I) directs the clinical psychology training program within the Duke Cancer Patient Support Program at the Duke Cancer Center. Both Drs. [name] and [name] are integrated into the psychosocial clinical care program at the Cancer Center and have experience referring cancer patients who are distressed to appropriate psychosocial or psychiatric care within this large team of mental health professionals. [name] will use these same resources when making referrals for distressed participants in this study. The PI and entire investigative team have conducted research in the proposed area and have not encountered significant psychological distress caused by study procedures. In fact, participation in the proposed study procedures and intervention is associated with few negative side effects and potentially multiple benefits to physical health, mood, and quality of life. The proposed significance of study findings outweighs the limited

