patients with chronic disease. They will be trained, specifically in the context of this trial, to monitor for any signs that participants are experiencing high levels of physical or emotional distress that need to be addressed outside the context of this trial. If this is determined to be the case, the PI will work directly with the participant to move forward in a way that is in the best interest of the patient. No participant will be kept in the trial if they are experiencing increased or extreme distress. Interventionists in this trial will be carefully trained to monitor participants' psychologist status and report to the PI. [name] (PI) will be contacted when emotional distress is identified in a participant. [name] works directly with the Cancer Patient Support Program at the Duke Cancer Institute as a practicing licensed clinical psychologist and as a supervisor to psychology trainees (i.e., advanced graduate students, clinical psychology interns); she is integrated into the psychosocial care program at the cancer center and has experience referring cancer patients who are distressed to appropriate psychosocial or psychiatric care within this large team of mental health professionals. She will use the same resources when making referrals for distress participants in this study.

There is the possibility of a breach of confidentiality. The consent form will address this possibility. All efforts will be made for confidentiality to be maintained by using case numbers to identify participants' research records and by having a limited number of individuals who have access to identifying information. Identifying information will be kept separate from research records. All research records will be kept in a locked file cabinet and password protected computer files. Only the PI and other trained research staff will have access to the research records. The PI has completed Duke University Health System Institutional Review Board's online training course: Protecting Research Subjects, which addresses confidentiality. All other individuals involved in this study will be required to complete this course and ongoing training.

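### Adverse-event capture is passive and depends on staff contact, which is greater in PCST-Video, so events in PainPac are likely to be under-recorded

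*Combined protocol and SAP*

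**What the plan says.** Data & Safety Monitoring gives the capture route: "All research personnel who have direct contact with patients will be trained to observe and report any adverse event to the principal investigator (PI". Data Safety Management Reporting repeats it. Reporting onward to the IRB and the data safety officer is in real time, with a quarterly internal report and an annual review. No section visible to us describes a scripted question, checklist or fixed time at which patients are asked about events.

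Contact with staff differs by design. Under Design & Procedures, PCST-Video patients "will receive 4 behavioral cancer pain intervention sessions delivered by videoconferencing", and "Sessions will be scheduled weekly for 45-60 min and mimic in person sessions". PainPac consists of four self-run modules of 8 minutes. Background & Significance gives the absence of a therapist as the app's rationale: "A standalone app would eliminate the need for a therapist, be available to the patient at all times".

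Interventionists carry an explicit reporting duty: "Interventionists will be trained to report any concerns immediately and directly to the PI" (Adequacy of Protection Against Risks, Emotional Upset) and "Interventionists in this trial will be carefully trained to monitor participants' psychologist status and report to the PI" (Data Safety Management Reporting). Only PCST-Video patients have an interventionist.

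Assessments are on one schedule: "PCST-Video participants will complete assessments at the same intervals as PainPac participants". They need not involve staff: "Patients may enter assessment data via the study mobile app or on their own online or by phone with a study team member" (Data & Safety Monitoring, Mobile App Data Storage and Security).

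**The concern.** When events are recorded only if a staff member hears of them, the count in an arm reflects both the events that occur and the chances to mention them. Here those chances are greater in the arm with a therapist. At equal true risk, the expected recorded count is then lower in PainPac.

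Two things are at stake. First, PainPac has not been tested as a standalone intervention, and it is the arm in which events are least likely to be heard. Real-time reporting and safety-officer review cannot act on an event that nobody heard of. Second, the pilot is meant to inform a larger trial. If events are tabulated or read by arm for that purpose, unequal capture may favour the app.

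**Working it through.** The documents give no event rate, detection rate or safety sample size, so there is no figure to reproduce. The check is a count of contacts followed by an illustrative model.

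**Inputs from the documents**
- Therapist sessions: 4 in PCST-Video, 0 in PainPac (Design & Procedures). Live session time is 4 × 45 = 180 to 4 × 60 = 240 minutes, against none.
- Assessments after randomization: 2 in each arm (A2 and A3).
- Patients per arm: 30 (Data Analysis & Statistical Considerations).

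**Scheduled opportunities for an event to be heard (k)**
- Counting A2 and A3 as opportunities: 4 + 2 = 6 in PCST-Video, 0 + 2 = 2 in PainPac.
- If A2 and A3 are self-completed and contain no event item: 4 against 0, apart from unscheduled contacts.

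**Model.** Let q be the chance that an event is mentioned at one opportunity. The share of events heard is 1 − (1 − q)^k. The documents give no value for q; 0.1 to 0.5 is assumed.

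| q (assumed) | PainPac, k = 2 | PCST-Video, k = 6 | Ratio |
|---|---|---|---|
| 0.1 | 1 − 0.9² = 0.19 | 1 − 0.9⁶ = 0.47 | 0.41 |
| 0.2 | 1 − 0.8² = 0.36 | 1 − 0.8⁶ = 0.74 | 0.49 |
| 0.3 | 1 − 0.7² = 0.51 | 1 − 0.7⁶ = 0.88 | 0.58 |
| 0.5 | 1 − 0.5² = 0.75 | 1 − 0.5⁶ = 0.98 | 0.76 |

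The ratio is recorded events in PainPac over PCST-Video at the same true risk.

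**Chance variation.** Recorded counts are taken as Binomial(30, true rate × share heard), with an assumed true rate of 10-30% in both arms. Across the four values of q, PainPac records fewer events than PCST-Video with probability 54%-85%, and more with probability 8%-29%. With full capture in both arms, the chance of fewer is 41%-44%.

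**Limit of the model.** The 6-against-2 count applies to an event early enough to be mentioned at every opportunity. After two sessions have passed, the count is 4 against 2 and the ratio is 1/(1 + (1 − q)²): 1/1.81 = 0.55 at q = 0.1 and 1/1.25 = 0.80 at q = 0.5. After the last session it is 2 against 2, and after A2 it is 1 against 1, so the ratio is 1. The imbalance therefore belongs to the treatment weeks. In the other direction, counting a self-completed assessment with no event item as an opportunity is generous to PainPac.

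**The case against.** The strongest reply is that the plan contains no safety comparison to be biased. Safety is not an aim or hypothesis. The measures compared between arms are feasibility, burden, acceptability, engagement and pain-related outcomes. The DSM report lists events by relatedness and handling, with no stated split by arm. This stands, and it limits the consequence to later reading of the counts. It does not answer the other problem, that an event in PainPac may never be heard at all.

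Second, PainPac patients are not out of contact. Staff confirm the app download and make technology check-ins (Design & Procedures, Randomization). Staff, as well as interventionists, are taught to monitor for physical and emotional distress. Coordinators review all assessments daily in both arms, with attention to suicidal ideation, and the investigator is told of any distress. Aim 3 plans post-treatment interviews, and PainPac alone collects daily pain ratings. All of this stands, and it covers part of the main psychological risk that the plan names. But the number and timing of check-ins and the number of interviews are not stated, no event question is described for either, and the stated use of the daily ratings is messaging. What remains uncovered is mainly events other than distress, and distress between assessments.

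Third, the assessment contents are in an attached Data Dictionary that we have not seen. If it holds an event item at A2 and A3, most of this point is answered.

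Fourth, the plan expects few events and defines an adverse event as causally related to the protocol, so counts may be very small. That is fair. However, the DSM report also provides for events that are not study-related; the two passages must be reconciled.

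**Conclusion.** The point holds in limited form. As described, capture is passive, planned live contact is unequal, and no common event question is visible, so events in PainPac are likely to be under-recorded relative to PCST-Video. Under the assumed q of 0.1-0.5 and 6 against 2 opportunities, PainPac would record about 0.41-0.76 of the PCST-Video count at equal true risk. The range rests on those assumptions and on nothing in the documents. It is also nearer 1 for events late in treatment.

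A reader might infer that the app will look safer. The documents do not support that certainty: no by-arm safety result is planned, distress is screened alike in both arms, and with 30 per arm PainPac could still show more events (8%-29% in the model). A reader might also reach a four-fold difference by assuming that 20% of patients have an event and that detection is 80% with a therapist and 20% without: 30 × 0.20 × 0.80 = 4.8 against 30 × 0.20 × 0.20 = 1.2. That ratio is only one assumed detection rate divided by the other.

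The change is worth making because it is cheap and the weaker capture falls on the untested standalone arm.

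**What to change.** First check the Data Dictionary. If A2 and A3 already contain an event item in both arms, cite it in Data & Safety Monitoring. If not:

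- Add the same short scripted question to A2 and A3 in both arms, asking about any new or worse medical or emotional problem since the last assessment.
- Record the source of each event: solicited, in-session or volunteered.
- Base any by-arm summary on solicited events. List events known only from therapist sessions separately. Real-time reporting stays as planned for all sources.

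Solicited opportunities are then 2 in each arm, so the expected ratio is (1 − (1 − q)²)/(1 − (1 − q)²) = 1.00 at equal true risk for any q. This requires that q and the completion of A2 and A3 be similar in both arms.

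The cost is slightly longer assessments and a few more events to review. A chart check for admissions and deaths is optional. It fits the plan's causal definition of an adverse event less well, since many such events would come from the cancer itself.
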